9.2.3.7 Risks of Anesthesia

Local Anesthesia

All biopsy procedures require local anesthesia using lidocaine, xylocaine, or related compounds. There is a small risk of an allergic reaction associated with these drugs. In order to minimize the risk of local anesthesia, only qualified personnel will perform the biopsy procedure. Patients will be queried if they have had previous allergic reactions to local anesthetics.

Intravenous Conscious Sedation

Certain biopsy procedures, such as lymph node, liver, or bone biopsies, may require intravenous conscious sedation (IVCS). IVCS is a minimally depressed level of consciousness that retains the patient's ability to maintain a patent airway independently and continuously and respond appropriately to physical stimulation and verbal commands.

The risks of intravenous conscious sedation include: inhibition of the gag reflex and concomitant risk of aspiration, cardiopulmonary complications (myocardial infarction, cardiac arrhythmias, hypoxemia), and allergic reactions to the sedative or analgesic medications. These risks are small but real; for example, in a prospective study of 14,149 patients undergoing IVCS during upper gastrointestinal endoscopies, the rate of immediate cardiopulmonary events was 2 in 1000⁴⁷. The 30-day mortality was 1 per 2,000 cases. In this study, there was a strong association between lack of monitoring and use of high-dose benzodiazepines with adverse outcomes. There was also an association between the use of local anesthetic sprays to the oropharynx and the development of pneumonia. In order to minimize the risk of intravenous conscious sedation, only qualified personnel will be responsible for conscious sedation. A minimum of two individuals will be involved in the care of patients undergoing conscious sedation-the physician performing the biopsy procedure, and

the individual (M.D. or R.N.) who monitors the patients and his/her response to both the sedation and the procedure, and who is capable of assisting with any supportive or resuscitative measures. The room where the procedure utilizing IVCS takes place will have adequate equipment to provide supplemental oxygen, monitor vital signs, and maintain an airway should this be necessary. An emergency cart will also be immediately accessible to the room where the procedure is to take place, and emergency support services will be available on page. Patients will be screened and evaluated for their fitness to undergo conscious sedation by a trained physician. Patients with active cardiac disease are excluded from this study. No local anesthetic spray to the oropharynx will be necessary, given that endoscopy is not a planned procedure. Following the procedure, patients will be observed closely in the recovery room for a minimum of 2 hours.

General Anesthesia

Because of the higher risk of general anesthesia compared with local anesthesia or intravenous conscious sedation, biopsies that would require general anesthesia in order to be performed *arenot permitted* on this protocol, unless they are being done for clinical reasons, and excess tissue that otherwise would have been discarded is then banked for the purpose of this protocol.

9.2.3.8 Cyclic Immunofluorescence Analysis

Cyclic immunofluorescence (cyCIF) will be performed on paired biopsy specimens to characterize immune cell (lymphocyte and myeloid) populations and their spatial relationship. There are a total of eight participants who have these tissues available in whom this analysis will be performed. Deidentified biopsy specimens will be shared with Harvard Medical School, specifically the laboratory of [name]. Any leftover specimens and all data generated from this will be returned to and become property of DF/HCC.

10. STUDY CALENDAR

Baseline evaluations are to be conducted within 1 week prior to start of protocol therapy unless otherwise specified. Informed consent, scans and x-rays must be done \leq 4 weeks prior to the start of therapy. In the event that the participant's condition is deteriorating, laboratory evaluations should be repeated within 48 hours prior to initiation of the next cycle of therapy.

Assessments must be performed prior to administration of any study agent. Study assessments and agents should be administered within \pm 3 days of the protocol-specified date, unless otherwise noted. End of treatment assessments may be performed within 30 days of treatment discontinuation.

	Baseline	Cycle 1 Day 1	Cycle 2 Day 1	Cycle 2 Day 21	Cycle 3 Day 1	Cycle 4+ Day 1	Cycle 4+ Day 21	End of Treatment	Follow-Up ¹
AZD1775 ^a			X		X	X			
Cisplatin ^b		X	X		X	X			
Informed consent	X ^m								
Demographics	X								
Medical history	X								
Physical exam	X	X	X		X	X		X	
Vital signs ^c	X	X	X		X	X		X	
Weight ^d	X	X	X		X	X		X	
Height	X								
Performance status	X	X	X		X	X		X	
Adverse Event Assessment		X	X		X	X		X	
CBC w/diff, plts	X	X	X		X	X		X	
Serum chemistry ^e	X	X	X		X	X		X	
B-HCG ^f	X								
EKG ^g	X							X	
Radiologic evaluationh	X			X			X		X
Archival tumor tissue	X								
Research biopsyi		X	X						
cfDNA Blood collection ^j	X				\mathbf{X}^{j}	\mathbf{X}^{j}		X ^j	
Blood for genomic sequencing ^k		X						vole. Day 1 docing is	

- a. AZD1775: 200mg (PO) BID beginning with Cycle 2 Day 1. The patient will take 5 doses of AZD1775 each cycle. Day 1 dosing is to be done in the clinic; subsequent doses can be taken at home. The 4 additional doses of AZD1775 are to be taken in approximately 12 hour increments. Patients should take AZD1775 either two hours before or two hours after a meal.
- b. Cisplatin: 75mg/m² (IV) given on Day 1 of each 21-day cycle (+/- 3 days)
- c. Vital signs should be collected pre-dose on dosing days and are to include measurements of heart rate, respiratory rate, systolic and diastolic blood pressure while the patient is in a seated position, and oral or tympanic temperature.
- d. Weight adjustments for cisplatin will be done according to institutional standards.
- e. Albumin, alkaline phosphatase, total bilirubin, bicarbonate, BUN, calcium, chloride, creatinine, glucose, LDH, phosphorus, potassium, total protein, SGOT [AST], SGPT [ALT], sodium, magnesium
- f. Serum pregnancy test (women of childbearing potential as defined in the eligibility criteria).
- g. A standard, triplicate12-lead EKG will be collected baseline. A standard, single EKG will be collected at the end of treatment. EKGs may be collected during protocol treatment if clinically indicated.
- h. Radiologic measurements should be performed every 2 cycles/6 weeks (+/-7 days). Participants who have their treatment held or delayed will continue to have restaging scans that align with cycles of treatment received, rather than weeks on study. Participants taken off study for reasons other than progressive disease should continue to have radiologic assessments completed every 6-9 weeks until progression.
- i. All patients with tumors that is accessible to biopsy will undergo research biopsies 5-48 hours after cisplatin monotherapy (Cycle 1 Day 1) and after the combination therapy (Cycle 2 Day 3, 5-8hrs (+/- 24hr) after AZD1775). If dosing is delayed placing the biopsy outside of the allowable window, the biopsy should be rescheduled to be within the window. If not feasible, the biopsy should be obtained as close to within the window as possible.
- j. At baseline, restaging visits, and at time of progression, two 10 mL blood samples will be drawn into EDTA-containing "purple top" test tubes or Streck Tubes for cfDNA analysis. If sample collection is missed for any reason at baseline or at the time of progression then the sample should be drawn at a future appointment.
- k. Blood sample for genomic sequencing will be collected at Cycle 1 Day 1
- 1. Participants will be contacted q 6 months for survival.
- m. Informed consent must be provided before any study-specific procedures are performed and within 28 days of registration.

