- 3.1.11 Availability of a tissue block from initial breast cancer diagnosis and/or metastatic recurrence. If a tissue block is not available, 10-20 unstained slides may be provided as an alternative. If unstained slides will be provided, they should not be sent until specifically requested by the DFCI study coordinator. If archival tumor tissue is not available, a fresh biopsy may be performed.
- 3.1.12 All patients with biopsy-accessible disease must be willing to undergo paired research biopsies. These biopsies will occur 5-48 hours after the C1D1 cisplatin dose (ie. C1D2or C1D3) and 5-8hrs (+/- 24hrs) after the last dose of AZD1775 on C2D3. The exact timing of the biopsy relative to receipt of study treatment should be accurately recorded.
 - Biopsies may be done with local anesthesia or intravenous conscious sedation, according to standard institutional guidelines.
 - Research biopsies requiring general anesthesia are not allowed on this protocol unless a biopsy is being obtained simultaneously for clinical reasons, in the judgment of the patients' treating physician.
 - Patients who undergo an attempted on-treatment research biopsy and in whom inadequate tissue is obtained are still eligible to continue protocol therapy. They will not be required to undergo a repeat biopsy attempt.
 - If dosing is delayed placing the biopsy outside of the allowable window, the biopsy should be rescheduled to be within the window. If not feasible, the biopsy should be obtained as close to within the window as possible.
 - Fine needle aspirates (FNA) is not allowed
- 3.1.13 Female subjects of childbearing potential must have a negative serum pregnancy test at screening.
- 3.1.14 The effects of AZD1775 on the developing human fetus are unknown. Women of child-bearing potential and men must agree to use enhanced methods of contraception. All women are considered to be of childbearing potential unless they fulfill one of the following criteria at screening:
 - Post-menopausal defined as age ≥50 and amenorrheic for at least 12 months OR
 - Women age <50 if they have been amenorrheic for at least 12 months and have a serum follicle-stimulating hormone (FSH) and luteinizing hormone (LH) level in the postmenopausal range (per institutional standards).
 - If women have documentation of irreversible surgical sterilisation by hysterectomy, bilateral oophorectomy, or bilateral salpingectomy, or bilateral tubal ligation, they are considered post-menopausal.

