- 3.1.15 Appropriate contraception should be used from the time of screening, throughout the duration of study participation, and for four months after the last dose of AZD1775. Acceptable methods of contraception include abstinence, tubal ligation, intra-uterine devices, and vasectomised partner. All methods of contraception (with the exception of total abstinence) should be used in combination with the use of a condom by the male sexual partner for intercourse. Should a woman become pregnant or suspect she is pregnant while she or her partner is participating in this study, the participants treating physician should be informed immediately. Additionally, male patients should refrain from donating sperm from the start of dosing until 6 months after discontinuing AZD1775. If male patients wish to father children they should be advised to arrange for freezing of sperm samples prior to the start of study treatment.
- 3.1.16 Participant must be able to swallow pills.
- 3.1.17 Participant may not have a percutaneous endoscopic gastrostomy (PEG) tube or be receiving total parenteral nutrition (TPN).
- 3.1.18 Ability to understand and the willingness to sign a written informed consent document.

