http://medicine.iupui.edu/clinpharm/ddis/table.aspx; medical reference texts such as the Physicians' Desk Reference may also provide this information. As part of the enrollment/informed consent procedures, the patient will be counseled on the risk of interactions with other agents, and what to do if new medications need to be prescribed or if the patient is considering a new over-the-counter medicine or herbal product.

- 3.2.9 Participants who have an uncontrolled intercurrent illness, including, but not limited to, ongoing or active infection, uncontrolled hypertension, unstable angina pectoris, uncontrolled cardiac arrhythmia, congestive heart failure-New York Heart Association Class III or IV (Appendix B), active ischemic heart disease, myocardial infarction within the previous six months, uncontrolled diabetes mellitus, gastric or duodenal ulceration diagnosed within the previous 6 months, chronic liver or renal disease, or severe malnutrition. In addition, patients are ineligible if they have a psychiatric illness or a social situation that could limit their ability to comply with the study requirements.
- 3.2.10 Participants who have refractory nausea and vomiting, chronic gastrointestinal diseases, or previous significant bowel resection that would preclude adequate absorption of AZD1775.
- 3.2.11 Pregnant women are excluded from this study because AZD1775 is a Weel inhibitor agent with the potential for teratogenic or abortifacient effects.
- 3.2.12 Lactating or breastfeeding women are excluded because there is an unknown but potential risk for adverse events in nursing infants secondary to treatment of the mother with AZD1775, breastfeeding should be discontinued prior to being treated with AZD1775. These potential risks may also apply to other agents used in this study.
- 3.2.13 Known HIV-positive participants are ineligible because these participants are at increased risk of lethal infections when treated with marrow-suppressive therapy.
 - 3.2.14 Participant with mean resting corrected QT interval (specifically QTc calculated using the Fridericia formula [QTcF]) > 450 msec for males and > 470 msec for females, from 3 electrocardiograms (ECGs) performed within 2-5 minutes apart at study entry, or congenital long QT syndrome.

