5.2.2 Subsequent Cycles

- ANC must be $\geq 1000/\text{mm}^3$
- Hemoglobin must be ≥9mg/dl
- Platelets must be $\geq 75,000/\text{mm}^3$
- Serum creatinine ≤1.5 x ULN, or measured creatinine clearance (CrCl) ≥45 mL/min as calculated by the Cockcroft-Gault method or 24-hour measured urine CrCl ≥45mL/min
- Transaminitis must return to \leq grade 2
- Diarrhea must be resolved \leq grade 1.
- Nausea and Vomiting must return to ≤ grade 1
- Neurosensory must be \leq grade 2
- Other Treatment Related non-Hematologic Toxicity must return to ≤ grade 1

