5.3 Agent Administration

5.3.1 *AZD1775*

Dose: 200mg po bid x 5 doses

AZD1775 will be administered bid for two and a half days starting concomitantly with the administration of cisplatin with cycle 2. The patient will take the first dose of AZD1775 in clinic on cycle 2 day 1, and subsequent doses that cycle can be taken at home. On cycle 2 day 1 and subsequent day 1 visits, AZD1775 and cisplatin may be administered concurrently. There is no preferential order of administration. The subsequent 4 additional doses of AZD1775 are to be taken in approximately 12 hour increments. Participants should take AZD1775on an empty stomach and should not have food 2 hours before or 2 hours after the dose. If the participant misses a dose by < 6 hours from scheduled dose, the dose should not be made up. If the participant vomits after the administration of AZD1775, the dose should not be readministered. AZD1775 should not be crushed, chewed or dissolved in water.

Premedication:

All patients must receive a 5-HT3 antagonist prior to each dose of AZD1775. In addition, dexamethasone 4 mg PO will be given with each AZD1775 dose as a minimum on the first day of dosing AZD1775 of every 3-5 days dosing period, unless contraindicated or not well-tolerated. Dexamethasone or the 5-HT3 antagonist may be given by IV.

5.3.2 *Cisplatin*

Administration

- **Dose**: Cisplatin 75mg/m² IVB q3 weeks (every 21 days, plus minus 3 days for scheduling issues). Cisplatin may be administered according to institutional guidelines at participating sites. The preferred guidelines are as described below.
- Infusion time: 60 minutes.
- **Pretreatment hydration**: Hydration may be achieved by IV infusion of 1 liter of sodium chloride 0.9% (±potassium 20 meq) over 1-2 hours prior to Cisplatin infusion.
- **Pretreatment Magnesium Supplementation**: As needed, give prior to Cisplatin, Magnesium Sulfate 2 GM IV×1.
- Treatment: Ensure there is adequate urine output averaging at least 100cc/hr prior to Cisplatin infusion. As needed, give 12.5mg IVB of MANNITOL 25% 30 minutes prior to Cisplatin infusion. Mix Cisplatin in 100-500ml sodium chloride 0.9% and infuse IVB over 60 minutes. Post-treatment hydration: Participants should receive 1 liter of sodium chloride 0.9% (±potassium 20 meq) IV over 1-2 hours after Cisplatin administration.
- **Post-treatment hydration:** Participants should receive 1 liter of sodium chloride 0.9% (±potassium 20 meg) IV over 1-2 hours after Cisplatin administration.

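### The only scheduled pregnancy test is 21 to 28 days old when AZD1775 is first given at Cycle 2 Day 1, and no repeat is required (minor safety gap)

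*Combined protocol and SAP*

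**What the plan says.** Criterion 3.1.13 asks for one test: "Female subjects of childbearing potential must have a negative serum pregnancy test at screening". The B-HCG row of the Study Calendar carries a mark at Baseline and nowhere else. Its footnote f describes it as "Serum pregnancy test (women of childbearing potential as defined in the eligibility criteria"). The calendar places baseline evaluations within 1 week before protocol therapy unless another window is stated, and none is stated for B-HCG.

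Protocol therapy opens with a 21-day cycle of cisplatin alone. Section 5.3.1 then says "AZD1775 will be administered bid for two and a half days starting concomitantly with the administration of cisplatin with cycle 2". Criterion 3.2.11 gives the reason for the pregnancy exclusion: "Pregnant women are excluded from this study because AZD1775 is a Weel inhibitor agent with the potential for teratogenic or abortifacient effects".

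Section 5.2.2 lists what must be satisfied before later cycles: blood counts, renal function, transaminases, diarrhea, nausea and vomiting, and neurosensory toxicity. Its final item begins "Other Treatment Related non-Hematologic Toxicity must return to" and sets a limit of grade 1. No pregnancy result appears in the list.

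Criterion 3.1.15 supplies the other protections. On timing: "Appropriate contraception should be used from the time of screening, throughout the duration of study participation", continuing for four months after the last AZD1775 dose. On method: "All methods of contraception (with the exception of total abstinence) should be used in combination with the use of a condom" by the male partner. If a pregnancy occurs or is suspected, "the participants treating physician should be informed immediately".

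**The concern.** The test is timed to the start of protocol therapy, but the agent that motivates the exclusion arrives one cycle later. The result is therefore recent for the first cisplatin dose and three to four weeks old for the first AZD1775 dose. A pregnancy that began around or after the screening test would meet no scheduled test before that dose.

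What is at stake is fetal exposure to a drug that the protocol itself regards as potentially teratogenic or abortifacient. This is a patient-safety matter only. It has no bearing on response rate, sample size or error rates.

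**Working it through.** The plan states no figure for the age of the result, so there is none to reproduce. It follows from date arithmetic.

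**Inputs**
- Test to Cycle 1 Day 1: 0 to 7 days (Section 10, baseline window).
- Cycle 1 Day 1 to Cycle 2 Day 1: 21 days (Section 5.1).
- Scheduling tolerance: 3 days either way (Section 5.3.2; Section 10).
- Longest toxicity delay before therapy must stop: 21 days (Section 5.5).

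**Formula.** Age of result at first AZD1775 dose = days from test to Cycle 1 Day 1 + days from Cycle 1 Day 1 to Cycle 2 Day 1.

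| Case | Calculation | Age (days) |
|---|---|---|
| On schedule | 0 + 21 to 7 + 21 | 21 to 28 |
| With the 3-day tolerance | 0 + 18 to 7 + 24 | 18 to 31 |
| Tail case: full 21-day toxicity delay, tolerance not added | 0 + 42 to 7 + 42 | 42 to 49 |
| With the proposed test | sample that day or up to 3 days before | 0 to 3 |

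**Does anything else in the plan trigger a test before that dose?**
- The Cycle 2 Day 1 chemistry panel (calendar footnote e) does not include hCG.
- The calendar's 48-hour laboratory repeat applies only when the participant's condition is deteriorating, and it does not name B-HCG.
- Cycle 2 Day 1 does include a physical examination, vital signs, performance status and adverse event assessment, and the calendar requires assessments before any study agent. These are clinical checks, not pregnancy tests.

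**What the fix does in later cycles, on schedule.** At Cycle 3 Day 1 the newest result would be 0 + 21 to 3 + 21 = 21 to 24 days old. At Cycle 4 Day 1 it would be 42 to 45 days old.

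**Number of assays.** The ceiling is one per patient in the planned sample of 37 (Section 13.1), since only women of childbearing potential need it. Section 9.2.3.8 reports eight participants with paired biopsy tissue. The second biopsy follows Cycle 2 AZD1775 dosing, so those eight are already past the point of the test, which leaves at most 37 − 8 = 29. This is a loose ceiling: patients without accessible disease or with inadequate tissue may also be past Cycle 2, and the documents do not give their number.

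**The case against.** The strongest reply is that this is a design choice. Criterion 3.1.13 and the calendar agree, no section promises a test before AZD1775, and the documents set no maximum age for a result. That stands. A reader might infer that the protocol contradicts itself or breaks its own eligibility rule; the text does not support that.

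A second reply is that the safeguards already deal with conception during Cycle 1. Contraception runs from screening, a condom is added to every method except total abstinence, and a suspected pregnancy must be reported at once. A reader might also infer that detection rests on the patient's own report alone. That is too strong, because a clinician examines her and assesses adverse events before the Cycle 2 dose, and Section 5.5 lets the investigator stop treatment if her condition changes. These checks still fall short of a test. Section 6.2 says nearly all patients on cisplatin have moderate to severe nausea and vomiting, so an early symptom of pregnancy could be put down to treatment. Contraception that starts at screening also does nothing about a conception just before it.

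A third reply is that one extra test only moves the gap, since AZD1775 is given in every later cycle and the result ages again. This is correct and limits the benefit. The case for Cycle 2 specifically is that it is the first exposure to the named agent, and that a test about three weeks after screening would pick up a conception the screening test was too early to show. From Cycle 3 onward the existing safeguards remain the only protection.

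Finally, the upper end of 49 days needs both the earliest permitted test and the full toxicity delay after one cisplatin dose. It should not be read as typical.

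**Conclusion.** The gap is real and minor. On schedule, the only pregnancy result is 21 to 28 days old at the first dose of the agent that prompts the exclusion, and nothing in Section 5.2.2 or the calendar renews it.

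The residual risk is probably small, but that is a judgement. The documents give neither the number of women of childbearing potential nor a contraceptive failure rate, so the risk cannot be quantified. The point about a conception too recent to detect assumes that a serum test taken within days of conception can be negative; the documents do not discuss this. The number of patients who could still benefit is also unknown. The primary endpoint and the statistical conclusions are not affected.

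**What to change.** Keep the baseline test and make two changes.

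1. In the Study Calendar, add a B-HCG mark at Cycle 2 Day 1 for women of childbearing potential who have not yet received AZD1775.
2. In Section 5.2.2, add one line: before the first AZD1775 dose, these women must have a negative serum pregnancy test from a sample taken pre-dose that day or within the preceding 3 days.

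No later-cycle test is proposed.

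The cost is one assay per such woman, usually from the blood already drawn that day for the CBC and chemistry. If the result would not be back before the in-clinic dose, an earlier draw, possibly a separate visit, or a short dose delay would be needed. A delay could shift the Cycle 2 Day 3 biopsy, which calendar footnote i already allows to be rescheduled.

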1. OBJECTIVES

1.1 Study Design

This is a single-arm, two-stage Phase 2 study assessing the efficacy of AZD1775, a Wee1 tyrosine kinase inhibitor, given in combination with cisplatin chemotherapy. The population to be studied will consist of approximately 35 patients with metastatic triple-negative breast cancer who have received 0 to 1 line of chemotherapy in the metastatic setting. All patients must have measurable disease at baseline and have archival tissue available. Treatment will consist of one cycle of cisplatin monotherapy (cisplatin 75 mg/m2 IV x1) followed by combination therapy of AZD1775 plus cisplatin starting 21 days later. AZD1775 will be administered as twice daily oral dosing (AZD1775 200 mg po bid) x 5 doses over 2.5 days, in combination with cisplatin 75 mg/m2 IV every 21 days. At least 10 patients will undergo a research biopsy within 5-48 hours after cisplatin monotherapy and then again within 5-8 hours after the last dose of AZD1775 in cycle 2 of cisplatin +AZD1775. Patients will undergo restaging scans every 6 weeks, those with complete responses, partial responses, and stable disease, will continue to receive study treatment. Patients with progressive disease will be taken off study.

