5. TREATMENT PLAN

5.1 Treatment Regimen

Treatment will consist of one cycle (21 days) of cisplatin monotherapy (cisplatin 75 mg/m2 IV) followed by combination therapy of AZD1775 plus cisplatin starting 21 days later. AZD1775 will be administered as twice daily oral dosing (AZD1775 200mg po bid) x 5 doses for 2.5 days, in combination with cisplatin 75 mg/m2 IV every 21 days. Cycle length is 21 days long. Treatment will be administered on an outpatient basis. Reported adverse events and potential risks are described in Section 7. Appropriate dose modifications are described in Section 6. No investigational or commercial agents or therapies other than those described below may be administered with the intent to treat the participant's malignancy.

	Regimen Description				
Agent	Premedications; Precautions	Dose	Route***	Schedule	Cycle Length
AZD1775*	See Section 5.4	200 mg	PO	Twice daily x 5 doses From Cycle 2	21 days (3 weeks)
Cisplatin	See Section 5.3.2	75 mg/m2	IV 60 minutes	Days 1 From Cycle 1	

* The participant will be requested to maintain a medication diary of each dose of medication. The medication diary will be returned to clinic staff at the end of each cycle.

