5.5 Criteria for Taking a Participant Off Protocol Therapy

Duration of therapy will depend on individual response, evidence of disease progression and tolerance. In the absence of treatment delays due to adverse event(s), treatment may continue until one of the following criteria applies:

- Disease progression
- Intercurrent illness that prevents further administration of treatment
- Unacceptable adverse event(s)
- Treatment delay of > 21 days due to toxicity
- Participant demonstrates an inability or unwillingness to comply with the medication regimen and/or documentation requirements
- Participant decides to withdraw from the protocol therapy
- General or specific changes in the participant's condition render the participant unacceptable for further treatment in the judgment of the treating investigator

Participants will be removed from the protocol therapy when any of these criteria apply. The reason for removal from protocol therapy, and the date the participant was removed, must be documented in the case report form (CRF) and entered in the Clinical Trial Management System (OnCore). Alternative care options will be discussed with the participant.

In the event of unusual or life-threatening complications, treating investigators must immediately notify [name] MPH at [contact].

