11. MEASUREMENT OF EFFECT

11.1 Antitumor Effect – Solid Tumors

For the purposes of this study, participants should be re-evaluated for response every 2 cycles of treatment or approximately every 6 weeks.

Response and progression will be evaluated in this study using the new international criteria proposed by the Response Evaluation Criteria in Solid Tumors (RECIST) guideline (version 1.1) [Eur J Ca 45:228-247, 2009]. Changes in the largest diameter (unidimensional measurement) of the tumor lesions and the shortest diameter in the case of malignant lymph nodes are used in the RECIST criteria.

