13.2 Analysis of Primary Endpoints

For this phase II trial, the analysis population is all patients who initiate protocol regimen. All patients who receive at least one dose of protocol regimen will be evaluable for objective response every 6 weeks from the time of their first treatment. The primary analysis will evaluate the objective response rate per RECIST 1.1. We will estimate this percentage and a corresponding 95% confidence interval (CIs) will be calculated.

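### Restaging follows cycles received in some sections and calendar weeks in others; under the cycle rule, toxicity delays push scan-detected progression, and so mean PFS, modestly later

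*Combined protocol and SAP*

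**What the plan says.** The imaging schedule is given in several places.

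- **Section 1.1:** "Patients will undergo restaging scans every 6 weeks", with no reference to cycles.
- **Section 13.2:** treated patients are "evaluable for objective response every 6 weeks from the time of their first treatment". This is a calendar anchor.
- **Section 11.1:** re-evaluation "every 2 cycles of treatment or approximately every 6 weeks", which allows either reading.
- **Section 10, footnote h:** "Radiologic measurements should be performed every 2 cycles/6 weeks (+/-7 days"). Held or delayed participants instead have "restaging scans that align with cycles of treatment received, rather than weeks on study". Those taken off for reasons other than progression are imaged every 6-9 weeks.
- **Section 10, calendar columns:** imaging sits at Day 21 of Cycle 2 and in the Cycle 4+ Day 21 column, so it is placed by cycle.
- **Section 6.1:** if Day 1 dosing slips, all assessments slip with it. This agrees with footnote h.

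The PFS definitions in Sections 11.1.6 and 13.3 run from registration or enrollment to progression or death. Section 11.1.6 censors at the last disease evaluation, and Section 13.3 plans a Kaplan-Meier estimate. Neither section has a rule for late or unevenly spaced scans.

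**The concern.** Once a cycle is delayed, a site cannot follow both footnote h and a six-week schedule counted from first treatment. The choice matters because scan-detected progression takes the date of the scan. If toxicity postpones the scan, toxicity also postpones the recorded event, and the observation schedule comes to depend on how well the patient tolerated treatment.

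Delays are foreseeable from the protocol itself. Section 6.2 reports myelosuppression in 25 to 30% of cisplatin-treated subjects, with nadirs on days 18 to 23 and most recovering by day 39, while the next dose falls due on day 22. Section 6.1 holds AZD1775 for Grade 2 neutropenia or thrombocytopenia.

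PFS is the first secondary objective. At stake are the accuracy of its estimate and the fairness of setting it beside trials that image on calendar time.

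**Working it through.** **Inputs from the documents**
- Cycle length: "Cycle length is 21 days long" (Section 5.1).
- Limit on delay: protocol therapy ends for "Treatment delay of > 21 days due to toxicity" (Section 5.5).
- First on-treatment scan: Cycle 2 Day 21 (Section 10).

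**1. The plan's own equation of two cycles with six weeks.** 2 x 21 = 42 days = 6 weeks. It reproduces, but only with no delay.

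**2. Intervals under footnote h.** Only Cycle 2's delay can move the first scan, so it falls at 42 + d days. A later interval contains two cycle starts and lasts 42 + d1 + d2 days.

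| Delay per cycle | First scan | Later interval, both cycles delayed |
|---|---|---|
| 0 days | 42 days (6 weeks) | 42 days (6 weeks) |
| 7 days | 49 days (7 weeks) | 56 days (8 weeks) |
| 14 days | 56 days (8 weeks) | 70 days (10 weeks) |
| 21 days | 63 days (9 weeks) | 84 days (12 weeks) |

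The +/-7 days comes on top. The last row is a boundary case: Section 5.5 stops therapy for delays beyond 21 days, whereas Section 6.2 (Other Toxicity) takes patients off protocol when toxicity results in a three-week delay. The two differ on a delay of exactly three weeks and must be reconciled.

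**3. Detection lag at a fixed interval.** Assume exponential progression times with median m, rate r = ln 2 / m, and progression dated at the next scan. The mean lag for interval L is L / (1 - exp(-rL)) - 1/r. For m = 13 weeks, r = 0.0533 per week, and L = 6 gives 6 / 0.2738 - 18.76 = 3.16 weeks. Across medians of 12-26 weeks the mean lag is 3.1-3.2 weeks at L = 6, 4.7-4.9 at L = 9 and 6.3-6.7 at L = 12.

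**4. Cycle-aligned against calendar scans.** This was simulated with 200,000 progression times per scenario, counted from first treatment, with delays drawn independently for each cycle from Cycle 2 on. Delay frequencies and medians are assumptions.

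| Delay pattern | Assumed median PFS | Rise in mean observed PFS |
|---|---|---|
| 30-50% of cycles, 0-3 weeks | 12-26 weeks | 0.5-0.8 week |
| 30% of cycles, 1-3 weeks | 8.7-26 weeks | about 0.7 week |
| 50% of cycles, 1-3 weeks | 8.7-26 weeks | 1.0-1.1 weeks |
| Every cycle, 1 week | 8.7-26 weeks | 0.9-1.0 week |
| Every cycle, 3 weeks | 8.7-26 weeks | 2.7-2.9 weeks |

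The mean shift was positive in every scenario. The median was not consistent, because it lands on the scan grid. With 30% of cycles delayed 1-3 weeks, the observed median fell from 18.0 to 16.5 weeks when the true median was 13, and rose from 18.0 to 20.9 when it was 17.3.

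**5. Primary design.** The Simon rule (continue with at least 4 of 17, succeed with at least 11 of 37) gives exact alpha 0.0948 and power 0.9033, matching the stated 0.095 and 0.903. Scan timing does not enter that calculation.

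**The case against.** The strongest reply is that cycle alignment is the working rule and a deliberate one. Footnote h speaks directly to delays, Section 6.1 and the calendar columns support it, Section 11.1 permits it, Section 1.1 is a synopsis, and Section 13.2 mainly describes who is evaluable. There is also a substantive reason for it. Cycle 1 is cisplatin alone, so scanning after Cycle 2 ensures that the first response assessment follows a combination cycle. If Cycle 2 is delayed 21 days it starts 21 + 21 = 42 days after Cycle 1 Day 1, and a week-6 calendar scan would fall at about the first AZD1775 dose.

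Much of this stands. A reader might infer that footnote h is a lone departure from a schedule fixed everywhere else; the sections just listed do not support that. The exposure argument is fair, but it applies only near the maximum Cycle 2 delay, so it is a caveat on the fix. It does not remove the conflict with Sections 1.1 and 13.2, or supply a PFS rule for uneven scans.

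It is also fair that the usual effect is small, at or below about the +/-7-day scan window; that deaths are dated correctly; that scans prompted by symptoms are not modelled; and that a single-arm trial has no between-arm bias.

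**Conclusion.** The inconsistency is real and worth correcting. Its effect is modest: a rise of roughly 0.5 to 1 week in mean observed PFS if 30-50% of cycles are delayed by up to 3 weeks, concentrated in the delayed patients. This rests on assumed delay rates, exponential PFS and progression dated at the scan. The 6-9 week interval after coming off for other reasons adds further unevenness, which was not modelled.

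Three stronger readings are tempting but unsupported.

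- **That restaging will typically stretch to 12 weeks.** This needs both cycles of a pair delayed to the limit, which Section 6.2 may not allow. The first scan can reach only about week 9.
- **That the comparison of genomic subgroups is biased.** This is possible only if tolerability differs by genotype, and the documents offer no evidence of that. The sequencing analysis in Section 2.5 covers only DFCI participants with existing data, and Section 9.1 calls the biomarker analyses exploratory.
- **That median PFS is necessarily inflated, or the trial's conclusion compromised.** The median can move either way, and the decision rule in Section 13.1 uses response counts alone.

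**What to change.** Reconcile Sections 1.1, 6.1, 10 (calendar columns and footnote h), 11.1 and 13.2 to one imaging schedule. The preferred form is every 6 weeks (+/-7 days) from Cycle 1 Day 1 until progression, whatever the holds or delays, with the same interval after treatment ends. Imaging must be exempted from the Section 6.1 rule that moves all assessments with dosing; amending footnote h and Section 11.1 alone would leave a new contradiction there and in the calendar columns.

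The cost is a short text amendment with three practical downsides. Scans and the cfDNA draws linked to restaging may not coincide with cycle visits. A few patients will have an extra scan. Where Cycle 2 is delayed close to 21 days, the first scan may fall at about the first AZD1775 dose, and such patients should be flagged in the ORR report.

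If cycle-aligned imaging is kept, correct Sections 1.1 and 13.2 to say so and prespecify an interval-censored sensitivity analysis of PFS. That costs one added analysis and needs the scan dates to be recorded.
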